#### 4.3. Premature Withdrawal from the Study

A patient has the right to withdraw from the study at any time, for any reason, and without repercussion.

The investigator and sponsor have the right to withdraw a patient from the study in the event of an intercurrent illness, AE, treatment failure, protocol violation, cure, and for administrative, or other reasons. Patients may also be withdrawn from the study, after appropriate counseling, for continued noncompliance with protocol-defined maximum NSAID use.

An excessive rate of withdrawals would render the study uninterpretable; therefore, unnecessary withdrawal of patients should be avoided.

Patients who withdraw prematurely from the study will be asked to complete study assessments per Section [6.2.10](#).

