- **Pre-Randomization Period (7 to 10 days before the randomization/baseline visit [day 1]):** Patients who meet the initial eligibility criteria, as assessed in the screening period, may enter the pre-randomization period. An in-office pre-randomization visit will occur for patients enrolled in the sub-study while a phone visit will occur if patients are only in the safety portion of the trial without the sub-study. The pre-randomization phone call or visit occurs 7 to 10 days before the randomization visit. Patients will stop taking/washout of their standard-of-care pain medications for OA during the pre-randomization period. In the event of inadequate OA pain relief, patients may take paracetamol/acetaminophen according to local standard-of-care, with a maximum daily dose of 2500 mg in Europe and 2600 mg in countries outside of Europe. Sub-study patients should discontinue use of paracetamol/acetaminophen 24 hours prior to the start of the randomization visit (baseline).

For any patient who had an MRI of any joint during screening, confirmation that there are no exclusionary findings on MRI must be received from the central reader before the patient can be randomized.

**Treatment Period 1 (starts with day 1 and continues through week 16):** The initial 16-week treatment period (treatment period 1) will begin at the randomization visit (baseline/day 1) and continue up to the week 16 visit. All patients will undergo baseline assessments at the day 1 visit and will be randomized to receive one of the ongoing study drug dose regimens (1 mg Q4W, 1 mg Q8W, or placebo). Patients randomized to 1 mg Q8W will receive alternating placebo injections at the monthly visits where active study medication will not be given to maintain the blind.

During treatment period 1, patients will be supplied with paracetamol/acetaminophen as the study-provided rescue medication. All patients will record rescue medication use in their diaries from the randomization visit through treatment period 1. All use of NSAIDs during treatment period 1, including oral or topical formulations, is prohibited (except up to 150 mg/day of aspirin/5-ASA, which is permitted for cardiac prophylaxis per local guidelines). Patients may be withdrawn from the study after appropriate counseling if they continue to use NSAIDs during treatment period 1.

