Safety assessments will be performed at each study visit during treatment period 1, as outlined in [Table 1](#). Potential events of adjudicated arthropathy will be monitored via clinical signs and symptoms of worsening joint pain during the study (eg, using the joint pain questionnaire and imaging). Potential events of sympathetic nervous system dysfunction will be monitored throughout the study through physical examination, AE reporting, assessment of orthostatic hypotension and via the Survey of Autonomic Symptoms.

Efficacy assessments will be performed for patients participating in the sub-study as outlined in [Table 3](#). Sub-study patients should discontinue use of paracetamol/acetaminophen 24 hours prior to the start of study visits during treatment period 1 in order to minimize the confounding effects of the rescue medication on efficacy measurements.

- **Treatment Period 2 (starts with study drug administration at week 16 and continues through week 52):** Treatment period 2 begins at the week 16 visit and continues through the week 52 visit. Patients will continue to receive fasinumab 1 mg Q8W, 1 mg Q4W or placebo Q4W during this period. At the week 24 visit, X-rays of the hips, knees, and shoulders will be obtained. The last dose of study drug will be administered at week 48.

During treatment period 2, patients may use non-NSAID standard-of-care pain treatment as rescue treatment and limited use of oral NSAIDs for non-OA related pain or fever.

Non-steroidal anti-inflammatory drugs will be study-provided as tablets or capsules, and may be used for up to 10 days in an 8-week period, 30 days in a 6-month period, and 60 days in a 1-year period. Use of oral NSAIDs in excess of these amounts is prohibited. The daily dose should not exceed the recommended maximum daily dose per the product labeling. Topical NSAIDs are prohibited during treatment period 2. Patients may be withdrawn from the study after appropriate counseling if continued noncompliance with protocol-defined maximum NSAID use occurs.

Patients will continue to be supplied with paracetamol/acetaminophen during treatment period 2.

The use of paracetamol/acetaminophen and/or NSAIDs should be recorded daily by the patient in the patient's diary. All other pain medications will be obtained and used per local standard-of-care; their use will be reported as concomitant medication during regular study visits.

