### 5.2.2. Paracetamol/Acetaminophen and Non-Steroidal Anti-Inflammatory Drugs - Weeks >16

Study-provided paracetamol/acetaminophen is the only study-provided rescue treatment for OA pain during treatment period 2, with a maximum daily dose of 2500 mg in Europe and other countries where 500 mg strength tablets/capsules are available and 2600 mg in any countries outside of Europe where 325 mg strength tablets/capsules are available.

Beginning at week 16, patients may take non-NSAID standard-of-care therapy in addition to study drug, in the event of inadequate pain relief for OA pain. Patients may also use limited-use NSAIDs for non-OA related pain or fever after week 16.

Non-steroidal anti-inflammatory drugs will be provided as tablets or capsules. The daily dose of NSAIDs should not exceed the recommended maximum daily dose per the product labeling, and their use will be limited to:

- 10 days in an 8-week period
- 30 days in a 6-month period
- 60 days in a 1-year period

The amount of paracetamol/acetaminophen and NSAIDs used in the prior 24 hours will be reported by patients in their diary. Non-steroidal anti-inflammatory drug accountability will be conducted at the end of treatment visit. Non-steroidal anti-inflammatory drugs will be sourced by the sites and reimbursed by the sponsor unless country-specific regulations and customs

require a different approach. Use of all other NSAIDs, including other oral or topical formulations, is prohibited. After appropriate counseling, patients may be withdrawn from dosing for continued noncompliance with protocol-defined maximum NSAID use. During the follow-up period, patients may increase their dose of NSAIDs 16 weeks after their last dose of study drug. Additionally, patients who discontinue study medication during the treatment period should follow the protocol-specified NSAID requirements; however, the NSAID dose can be increased to standard of care doses 16 weeks after their last dose of study medication.

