#### **5.3.2. Study Drug Discontinuation**

Study drug may be permanently or temporarily discontinued due to medical need, as determined by the investigator, medical monitor, or the sponsor and according to the study stopping rules (Section 3.1.1).

Patients who permanently discontinue from study drug will be asked to remain in the study and to return to the clinic for all remaining study visits, per the visit schedule. Once patients discontinue from study drug, they can restart standard-of-care medications for the treatment of their OA pain with the exception of NSAIDs. Non-steroidal anti-inflammatory drugs can be restarted for OA pain 16 weeks after the last dose of study drug.

Patients who opt to withdraw from the study will be asked to complete the early termination visit per Section 6.2.10.

Patients who discontinue from study drug early due to a clinically relevant joint event (see Section 7.6.1.1) should return to the clinic for all remaining study visits per the visit schedule.

In the event that a patient must undergo JR surgery during the treatment or follow-up periods, they will be discontinued from study drug and asked to return to the study site for a pre-operative visit and for follow-up safety evaluations (as described in Section 6.3.4.10) 4 and 20 weeks after surgery. Pre-operative imaging (X-ray and MRI) will be obtained and submitted to the independent adjudication committee for review to ensure that an AA event is not in occurrence. Instructions for the submission process are provided in the study manual.

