##### **5.3.2.1. Reasons for Permanent Discontinuation of Study Drug**

Study drug dosing will be permanently stopped in the event of:

- A patient being randomized under amendment 3 or a subsequent amendment and treated with the 3 mg Q4W or 6 mg Q8W dosing regimen
- A patient being randomized under an earlier version of the protocol before amendment 3 and treated with the 6 mg Q4W, 9 mg Q4W, or placebo Q4W dosing regimen
- A subject developing clinically significant sensory and motor neurologic events confirmed by a neurologist's examination and graded by the neurologist as at least

moderate peripheral neuropathy limiting activities of daily living, ie, grade  $\geq 2$  according to v.4 (CTCAE); study sites should use CTCAE v.4 criteria throughout the study for consistency

- Evidence of pregnancy
- A patient developing new or worsening signs and symptoms indicative of carpal tunnel syndrome
- Continued noncompliance with protocol-defined maximum NSAID use (see Section 4.3) after appropriate counseling
- Continued noncompliance with protocol-defined maximum acetaminophen/paracetamol use (with a maximum daily dose of 2500 mg in Europe and other countries where 500 mg strength tablets/capsules are available and 2600 mg in any countries outside of Europe where 325 mg strength tablets/capsules are available) after appropriate counseling
- JR Surgery
- AESI:
  - Adjudicated arthropathy, as described in Section 7.6.1.1
  - Sympathetic nervous system dysfunction, as described in Section 7.6.1.2
- Hepatotoxicity
  - Study drug should be discontinued if:
    - a) Total bilirubin (TBL)  $>2x$  ULN or international normalized ratio (INR)  $>1.5$  and
    - b) Alanine aminotransferase (ALT) or aspartate aminotransferase (AST)  $>3x$  ULN and
    - c) No other cause for a and b is readily apparent

Other causes of ALT, AST, and TBL elevations can include alcoholic hepatitis, autoimmune hepatitis, non-alcoholic hepatitis, heritable diseases (Gilbert's Syndrome), heart failure, and viral hepatitis.

Study drug may be withheld in patients who do not meet criteria for permanently discontinuing study drug, until an alternative cause for drug-induced liver injury can be determined. The patient may be re-challenged if an alternative cause for elevated liver function tests is found and the liver function tests return to baseline, but only after discussion with the sponsor.

- Systemic hypersensitivity reaction assessed as related to study medication

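### For continued NSAID overuse after counselling, Protocol 5.3.2.1 makes the permanent dosing stop mandatory while 5.2.2 makes it optional

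*Protocol*

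**What the plan says.** **Dosing.** Protocol 5.3.2.1 opens its list with "Study drug dosing will be permanently stopped in the event of". One item on that list is "Continued noncompliance with protocol-defined maximum NSAID use (see Section 4.3) after appropriate counseling". Protocol 5.2.2, which sets the NSAID day limits for the period after week 16, says "After appropriate counseling, patients may be withdrawn from dosing for continued noncompliance with protocol-defined maximum NSAID use".

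**Study participation.** Protocol 4.3, the target of the cross-reference in 5.3.2.1, says "Patients may also be withdrawn from the study, after appropriate counseling, for continued noncompliance with protocol-defined maximum NSAID use". Protocol 3.1 says the same in substance for each treatment period: "Patients may be withdrawn from the study after appropriate counseling if they continue to use NSAIDs during treatment period 1" for period 1, when NSAIDs are prohibited apart from low-dose aspirin, and "Patients may be withdrawn from the study after appropriate counseling if continued noncompliance with protocol-defined maximum NSAID use occurs" for period 2.

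**Retention.** Protocol 5.3.2 sets the default after a dosing stop: "Patients who permanently discontinue from study drug will be asked to remain in the study and to return to the clinic". The synopsis and 6.2.7 agree with it. Section 4.3 itself adds that "unnecessary withdrawal of patients should be avoided". Sections 5.2.2 and 5.3.2 also say when NSAIDs may be resumed after study drug is stopped (16 weeks after the last dose), which presupposes that such patients are still being followed.

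**The concern.** The NSAID restriction is a stated risk control. Protocol 1.2 reports that joint damage was more frequent when NSAIDs were taken with anti-NGF drugs, and gives this as the reason for restricting co-use. The rule for a patient who will not comply is therefore a safety stopping rule, and sites need one answer.

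They get two. A site asking what to do about NSAID overuse is likely to look in 5.2.2, because the limits are there. That section makes the dosing stop discretionary and does not mention 5.3.2.1. A site that starts from 5.3.2.1 finds a mandatory stop, follows its pointer to 4.3, and arrives at a different action: optional withdrawal from the study. What is at stake is continued active dosing in patients whom the discontinuation section says must stop.

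The lesser issue is follow-up. Sections 3.1 and 4.3 name overuse as a ground for leaving the study, and no text says when a patient should leave rather than only stop drug. Withdrawal would end later scheduled joint imaging in patients the protocol regards as at higher risk. Joint events are among the primary safety variables (SAP 4.5.1).

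**Working it through.** The plan states no figure on this point, so the check is mainly a comparison of texts, followed by a short dose count.

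**Step 1. Same trigger, different force.**

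| Protocol section | Trigger | Action | Force |
|---|---|---|---|
| 5.3.2.1 | NSAID use above the limit, continued after counselling | permanent stop of dosing | mandatory |
| 5.2.2 (after week 16) | same | stop of dosing | optional |
| 4.3 | same | leave the study | optional |
| 3.1, period 2 | same | leave the study | optional |
| 3.1, period 1 | any continued NSAID use, after counselling | leave the study | optional |

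Rows 1 and 2 share trigger, counselling condition and action, and differ only in force. That is a direct conflict in current text. Rows 3 to 5 concern a different action, so they do not contradict row 1. Both can be followed at once: stop dosing, and decide separately about study participation.

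**Step 2. The cross-reference.** The 5.3.2.1 item points to 4.3 for what it means by the NSAID maximum. Section 4.3 gives neither the maximum nor a dosing rule. The limits are in 5.2.2 (10 days in 8 weeks, 30 in 6 months, 60 in 1 year). The period 1 prohibition is in 5.7.2.

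**Step 3. How much dosing the conflict could allow.** Inputs: injections every 4 weeks, last dose at week 48 (3.1, 5.1), and placebo alternating with active drug on 1 mg Q8W (5.1). Week 28 is an illustrative date for finding continued noncompliance.

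- Injections from week w through week 48: (48 − w)/4 + 1. For w = 28: 20/4 + 1 = 6 (weeks 28, 32, 36, 40, 44, 48).
- 1 mg Q4W: all 6 are active.
- 1 mg Q8W: with active drug on day 1, active doses fall at weeks 32, 40 and 48, so 3 of 6. Six alternating injections contain 3 active ones whichever comes first.

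Under 5.3.2.1 the count from the same date is 0.

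**Step 4. Does the SAP settle the point?** No. SAP 5.1.4 reports NSAID use above the limit in period 2 by arm, and 5.1.5.2 reports reasons for study withdrawal and for treatment discontinuation. Neither says which rule applies. SAP 5.1.8 plans sensitivity analyses of destructive arthropathy, and of destructive arthropathy with joint replacement, excluding NSAID users.

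**Step 5. Effect of lost follow-up on event rates.** This would need the share of overusers, the share of those withdrawn, and the rate ratio for joint events in overusers. The documents give none of the three, so no figure is offered.

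**The case against.** **The dosing harm is a worst case.** Six extra injections require a site to act on 5.2.2, overlook the dedicated discontinuation section, and dose at every remaining visit. Continued noncompliance after counselling is a matter of site judgement under either wording. Dosing is also withheld for worsening joint pain or suspicious imaging whatever the NSAID rule (5.3.2.2, 7.6.1.1). All of this stands, and it limits the size. It does not remove the conflict: once a site has judged the trigger met, one section requires the stop and the other leaves it open.

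**A reader might infer that the protocol contradicts itself on study withdrawal.** The documents do not support that. The clauses in 3.1 and 4.3 are permissive, 4.3 warns against unnecessary withdrawal, and the synopsis, 5.3.2 and 6.2.7 make retention the default. What remains is a tension and a missing criterion.

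**A reader might also infer that withdrawing overusers biases the joint safety comparison.** That is not supported either. The inputs are absent, no direction is established for fasinumab against placebo, and the effect may be negligible. An early termination visit with radiographs is requested (6.2.10, Table 2). Inclusion criterion 10 asks for willingness to supply joint-replacement information over the intended participation period, although it sets no procedure after withdrawal. Patients withdrawn for overuse are NSAID users, so they fall outside the SAP 5.1.8 sensitivity analyses, and their lost follow-up cannot affect those results. That cover is partial, because it does not extend to all adjudicated arthropathy.

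**Conclusion.** The dosing conflict is real and should be corrected. After week 16, with the same trigger and the same counselling condition, 5.3.2.1 requires a permanent stop and 5.2.2 permits one, and the cross-reference leads to a section with no dosing rule. Because the rule guards against a risk named in the protocol, this is more than a clerical slip.

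The size is bounded per patient: from week 28, at most six further injections (six active on 1 mg Q4W, three on 1 mg Q8W), assuming the site follows 5.2.2 and doses at every remaining visit. The number of patients affected is unknown, because the documents give no expected overuse rate.

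The study-withdrawal wording is a place to improve consistency, not an error.

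**What to change.** **Main change.** In 5.2.2, make withdrawal from dosing mandatory and permanent for continued NSAID noncompliance after counselling, with a reference to 5.3.2.1. In 5.3.2.1, point the cross-reference to 5.2.2 for the limits, and to 5.7.2 for the treatment period 1 prohibition, in place of 4.3.

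**Secondary change.** In 3.1 (both treatment periods) and 4.3, state that NSAID noncompliance leads to stopping study drug with continued follow-up under 5.3.2, unless the patient withdraws consent. State also that the protocol-violation ground in 4.3 is not to be used for NSAID overuse alone; otherwise the same route out of the study stays open. The general right to withdraw a patient for other reasons is unaffected. No new NSAID rule is needed, since the 16-week restart rule already covers retained patients.

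**Cost.** A protocol amendment with IRB/EC approval (Section 14) across the four listed regions. The main change is one verb and one cross-reference. It gives up on-treatment exposure only in patients whom 5.3.2.1 already says must stop. The secondary change keeps some noncompliant patients on visits already planned for them: each 1% of the 7000 planned is 0.01 × 7000 = 70 patients. No procedures are added.

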#### 4.4. Replacement of Patients

Patients prematurely discontinued from the study will not be replaced.

## 5. STUDY TREATMENTS

### 5.1. Investigational and Reference Treatments

Under amendment 8 and amendment 9, patients will be enrolled into the main safety study and randomized to 1 of the following treatment arms:

- Fasinumab 1 mg SC Q8W (patients will receive placebo injections at the study visits where fasinumab is not administered)
- Fasinumab 1 mg SC Q4W
- Placebo SC Q4W

Prior to amendment 7 (urgent safety measure), patients were randomized to 6 mg Q8W or placebo in the main study (after amendment 3), and to the following treatment arms in the efficacy sub-study (amendment 5):

- Fasinumab 1 mg SC Q8W (included in the efficacy sub-study only; patients will receive placebo injections at the study visits where fasinumab is not administered)
- Fasinumab 1 mg SC Q4W
- Fasinumab 3 mg SC Q4W
- Fasinumab 6 mg SC Q8W (patients will receive placebo injections at the study visits where fasinumab is not administered)
- Placebo SC Q4W

Enrollment into the efficacy sub-study was completed prior to amendment 7.

All patients previously enrolled into the main study had completed treatment prior to amendment 7. Under amendment 7, patients randomized to 3 mg Q4W or 6 mg Q8W in the efficacy sub-study were discontinued from study drug for the remainder of the study. All patients who were discontinued from study drug immediately entered the follow-up period.

Patients originally randomized to earlier versions of the protocol (prior to amendment 3) with 9 mg Q4W, 6 mg Q4W, or placebo Q4W were discontinued from study drug for the remainder of the study under an amendment 4EU (issued on 12 January 2017) and amendment 5 global (issued on 16 March 2017).

All patients will receive SC injections Q4W from day 1 up to week 48. All SC injections will be in the abdomen, thigh, or upper arm. Study drug (fasinumab or placebo) will be administered at the study site after all study visit procedures have been completed. Patients will be observed in the clinic for approximately 1 hour after study drug is administered.

Instructions for study drug administration are provided in the pharmacy manual.

Doses of study drug must be given within  $\pm 7$  days from the scheduled dose date. If the window is missed, the dose should not be administered. The next dose should be administered at the next scheduled dosing date.

## 5.2. Rescue Treatments

Rescue treatments will be provided to all patients according to Section 6.1.

### 5.2.1. Paracetamol/Acetaminophen - Weeks 1 through 16

Study-provided paracetamol/acetaminophen is the only allowable rescue treatment for OA pain during treatment period 1. In the event of inadequate relief for OA pain, paracetamol/acetaminophen may be taken as needed according to local standard-of-care, with a maximum daily dose of 2500 mg in Europe and countries with 500 mg tablets/capsules or 2600 mg in countries outside of Europe with 325 mg tablets/capsules. Sub-study patients should discontinue use of paracetamol/acetaminophen 24 hours prior to the start of the randomization visit (baseline) and prior to the start of scheduled study visits during treatment period 1 in order to minimize the confounding effects of the rescue medication on efficacy measurements.

The amount of paracetamol/acetaminophen used in the preceding 24 hours will be reported by patients from the randomization visit (day 1) using the patient diary. All patients will record rescue medication use starting at the randomization visit. Paracetamol/acetaminophen accountability will be conducted at each site visit starting at the week 4 visit. Paracetamol/acetaminophen will be sourced by the sites and reimbursed by the sponsor unless country-specific regulations and customs require a different approach.

Patients should be cautioned to avoid consumption of alcoholic beverages while taking paracetamol/acetaminophen and to take no more than the maximum daily allowable dose. For additional information regarding rescue medication, please refer to the study pharmacy manual.

